## 10.2 Data Management

In addition to and in combination with meeting HIPAA regulations, data collected and managed will be securely handled to prevent unauthorized access or modification. All those in the study staff who have access to data on those screened and/or participating in the study will follow these procedures when handling the data: (1) education about the need for security and confidentiality, (2) signing a confidentiality agreement, (3) using passwords to control access to the electronic databases and regular changing of passwords, (4) keeping paper versions of surveys and any other paper versions of screened/participating individuals' data in a locked room, & (5) servers will be protected by firewalls, McAfee Virus Scan Enterprise anti-virus software, daily full tape backups stored in a locked room, and encryption via the https protocol.

## 10.3 Data Accuracy

Data accuracy has two aspects in this trial: (1) accuracy of self-reported data by trial participants, and (2) accuracy of data management. The trial has procedures for both, which will be reviewed annually by the Project Manager and approved by the Principal Investigator.

## 10.4 Monitoring Data Quality and Integrity

Several procedures will be used to maintain data integrity. Participants and data collectors will complete all study assessments using a secure, metadata-driven system designed and tested by our software development team, which has been in use for the past five years for other research studies in which participants enter information about themselves. Surveys are hosted on a Web site running on the Apache web server on a Linux operating system behind the Fred Hutch firewall. Study participants who complete these online surveys will only have access to data that they have entered on in-process surveys. Participants may access partially completed surveys via a participant-specific link provided by email and entry of the participant's birthdate. Once surveys are complete, the data are inaccessible from the web site. Participants and others will be prevented from accessing any other data on the Web server by a number of operating system, web server, and application controls. Users will connect to the web site to complete the surveys via HTTPS using Transport Layer Security (TLS). Employment of the TLS protocol will prevent anyone from intercepting data passed between the end user's web browser and the web server. The data generated by the QuitBot CA program will be extracted over a secure connection on a weekly basis, and stored on a secure internal FH server. A raw copy of the data serves as an additional backup beyond the ongoing built-in Azure storage backup processes. Paper data will be kept in a locked cabinet. All databases will be stored in a centralized location at Fred Hutch on a secure server. Data will be backed up daily and access will be password protected and limited to persons working on the project. Persons will only have access to specific data required for their project tasks. Identifying information will be stored separately from the assessment data. Data will be audited on an ongoing basis to ensure confidentiality safeguards are being maintained and data integrity is being maintained. Data entry systems will be set-up to allow field checks, range checks for continuous variables, valid value checks for categorical variables, and checks for logical consistency of responses. All data entry and hand computations will be double-checked. Queries and data reports will be generated on a routine basis to monitor data quality.

## 11.0 STATISTICAL CONSIDERATIONS

### 11.1 Study Design

We planned to enroll 1520—and actually enrolled 1647—adult daily smokers who want to quit smoking. Participants will be randomly assigned (with 0.5 probability) to (1) the QuitBot conversational agent (CA) or (2) SmokefreeTXT text messaging. Based on evidence from text messaging trials meta-analyses [1], we will stratify randomization on biological sex (male vs. female), heaviness of smoking index score ( $\leq 4$  vs  $>4$ ), and percent confidence in being smoke-free in 12 months ( $\leq 70\%$  vs.  $>70\%$ ). Moderators will be measured at baseline, mediators at 3 and 6 months post randomization, and cessation and cost-effectiveness outcomes at 3, 6, and 12 months post randomization. Random assignments will be computer-generated after consent.

### 11.2 Primary/Secondary Endpoints/Hypotheses and Analytical Methods

[figure not shown]
The primary endpoint will be biochemically-verified 30-day point prevalence at 12 months post randomization. Secondary endpoints will be 30-day biochemically confirmed point-prevalence at 3 and 6 months post randomization. Consistent with remote digital cessation study methods [1, 18], biochemical confirmation will be conducted on participants self-reporting no smoking at all in the last 30 days.

Our primary outcome hypothesis is that QuitBot will have significantly higher 30-day point prevalence abstinence at 12 months post-randomization than SmokefreeTXT. For each comparison of the treatment arms on the primary and all secondary endpoints, we will use a logistic regression model. Using standard smoking cessation trial intent-to-treat analysis, all missing outcomes will be coded as smokers [31, 35-39]. The model will adjust for all stratification factors as well as baseline factors that are imbalanced after randomization and significantly related to the outcome. In addition, we will conduct these sensitivity analyses: (1) multiple imputation of missing outcomes [107-109], (2) complete case analysis of those providing follow-up data, (3) using a secondary cessation outcome of no use of cigarettes and other nicotine or tobacco products except FDA-approved nicotine replacement therapies, (4) adjusting for baseline usage of other tobacco and nicotine products, and (5) adjust for usage of other interventions and cessation medications after study enrollment.

[figure not shown]
### 11.3 Additional Efficacy Hypotheses, Outcome Measures, and Statistical Methods

**Conceptual model of conversational agents for smoking cessation**

Based on the Conceptual Model above, we hypothesize a serial multiple mediator model with two sets of mediators: the four therapeutic alliance processes ( $M_1$ ) and the three engagement indicators ( $M_2$ ). As shown in the figure below, we hypothesize that these mediators operate in a serial sequence: QuitBot's treatment assignment (but not SFT's) will impact therapeutic alliance processes (path  $a_1$ ), the therapeutic alliance processes will in turn impact treatment engagement variables (path  $d_{21}$ ), and the engagement variables will in turn impact the 12-month primary cessation outcome (path  $b_2$ ). The serial mediation model is summarized by three equations, which we will analyze using the bootstrap confidence interval method of the PROCESS analysis macro developed for SAS [110]: (1)  $M_1 = i_{M_1} + a_1X + e_{M_1}$ ; (2)  $M_2 = i_{M_2} + a_2X + d_{21}M_1 + e_{M_2}$ ; (3)  $Y = i_{M_2} + c'X + b_1M_1 + b_2M_2 + e_Y$ . Treatment assignment ( $X$ ) affects cessation outcome ( $Y$ ) through four pathways. There are three indirect pathways: (1) from  $X$  to  $Y$  through  $M_1$ , estimated by  $a_1b_1$ , (2) from  $X$  to  $Y$  through  $M_2$ , estimated by  $a_2b_2$ , and (3) from  $X$  to  $Y$  through both  $M_1$  and  $M_2$ , in sequence, with  $M_1$  affecting  $M_2$  [110], estimated by  $a_1d_{21}b_2$ . Finally, the fourth pathway is direct from  $X$  to  $Y$ , without passing through either mediator, estimated by  $c'$ . Finally, we will calculate the proportion of treatment effect explained by each of these mediators [111-113]. Number of participant engagements will be adjusted with poisson regressions that account for the number of prompts a participant received. A secondary model will examine whether therapeutic alliance processes impact cessation knowledge gained (path  $d_{21}$ ), and knowledge gained in turn impacts the primary cessation outcome (path  $b_2$ ).

We hypothesize that QuitBot will be cost-effective vs. SmokefreeTXT (SFT), as measured by cost per quitter, cost per life year gained, and cost per quality-adjusted life year (QALY) gained. Analyses: We will use current good practices of estimating cost-effectiveness [114], as applied to smoking cessation interventions [115]. To examine whether QuitBot costs less than SFT to help a person quit, we will estimate the incremental cost-per-quitter: difference in total cost of delivering the two interventions [116] divided by the difference in the number of 30-day abstinent participants at 12-months (Total CostQuitBot – Total CostSFT/# AbstinentQuitBot – # AbstinentSFT). Total cost assessments are described in Section C.5.5. Second, to estimate whether QuitBot represents good value vs. SFT per life year gained [115], we will calculate the standard metric of cost per life year gained as: Total CostQuitBot – Total CostSFT/# Life Years AddedQuitBot – # Life Years AddedSFT). Life years added attributable to each intervention's 12-month primary endpoint effect size will be derived from the life years estimates, reported in Stapleton & West [115], that conservatively account for gender, age, discounting, relapse, and unaided cessation. Lastly, to examine whether QuitBot represents good value vs. SFT per QALY [116], an additional analysis of the cost-per-QALY gained will be conducted as: (Total CostQuitBot – Total CostSFT)/(QALYQuitBot – QALYSFT). This analysis will be calculated by adding a Generalized Linear Model-based weighted quality of life parameter derived from the standard EQ-5D quality of life measure [96] taken at the 12-month endpoint. For the cost per life year and cost per QALY analyses, we will assess cost-effectiveness relative to implied willingness to pay in the U.S. of \$100,000 [117]. In each of the three analyses, we will conduct probabilistic sensitivity analyses with 5,000 Monte Carlo simulations that will derive a cost-effectiveness plane (and 95% CI ellipse) across a range of total costs and effect sizes [118]. Similar cost-effectiveness analyses will be conducted for these subgroups: biological sex (male vs. female), age (50 or older vs. 49 or younger), race/ethnicity (non-Hispanic white vs. all other races), and education (high school or less vs more than high school). All will adjust costs to 2019 U.S. dollars and discount future costs and benefits incurred after one year at 3% per annum as is recommended by the panel on cost-effectiveness [105, 119].

**Analysis of Sex as a Biological Variable:** Consistent with NIH guidelines [120], we will report data by sex, in order to the consider the potential influence of sex in the interpretation of study results. Specifically, for all the analyses described above, we will examine the estimated difference in effect sizes between men and women by incorporating interactions between treatment and sex in a regression model, or by separately analyzing results by sex. We will also stratify random assignment by sex.

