Smokefree comparison intervention: for initial evidence of whether CA is a fundamental shift beyond text messaging, SmokefreeTXT (SFT) is the ideal comparison. A 42-day program, SFT is the most widely accessible text messaging program in the US. It is non-proprietary and free to the public, thereby providing maximal accessibility and replicability. Daily messages are sent about the importance of quitting smoking, setting a quit date, preparing to quit, quitting, and maintaining abstinence. Daily messages check in about quit status. Three keywords can be sent by users to receive anytime help: “CRAVE” (on how to cope with urges), “MOOD” (on how to cope with moods triggering smoking), and “SLIP” (on how to cope with lapses). See Figure 3 for sample message. NCI’s SFT contractor (ICF International) provided us the full content of SFT so that we could internally host a secured private version for research. For blinding, the intervention was called “QuitBot.” Comparisons between QuitBot and SFT are shown in Table 2. In both SFT & QuitBot, participants receive two prompts per day (three on the quit day), with those not responding to prompts continuing where they left off.

[figure not shown]

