### Experimental Design Schema

#### 7.1 Duration of Therapy

Both therapies (the digital intervention programs) consist of 42 days of smoking cessation content.

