### 10.1 Source Data to be Recorded Directly

There are 6 sources of data for the study: (1) screening survey (2) baseline survey, (3) contact form, (4) 3-month follow-up survey, (5) 6-month follow-up survey, and (6) 12-month follow-up survey. We will also collect automated utilization data from the QuitBot CA program, Google Analytics, and SmokefreeTXT program. All data will be collected directly from consenting adult participants. A description of these sources of data follows.

**Survey Data.** The Baseline Survey, hosted on our secured recruitment website, will collect data on (1) demographics, (2) nicotine and tobacco use, (3) nicotine dependence, (4) readiness to quit, (5) quit attempts, (6) smoking costs, (7) quality of life, (8) interpersonal trust, (9) social support, and (10) contact information needed for the study's follow-up data collection activities – as well as information about whether or not it is acceptable to receive email or voice messages and mail from

the study. The 3-month survey will primarily collect data on intervention processes (e.g., therapeutic alliance), cessation progress (e.g., quit attempts) and outcomes (e.g., 30-day abstinence), and the participant's experiences with their assigned smoking cessation intervention. The 6- and 12-month surveys will primarily collect data on cessation progress/outcomes.

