**QuitBot CA utilization data and security.** The QuitBot CA program will be accessible to participants when they access the download and login link sent to them in their secure trial enrollment email. During the enrollment process, participants check their smartphone storage requirements and opt-in to download the app. If the participant is then randomized to the QuitBot arm, a randomly-generated opt-in ID is sent to the QuitBot backend, where it is whitelisted and connected to their user data, which allows them to fully interact with the bot content. Non-whitelisted users who attempt to download the app will not be able to login and will receive a single generic response, redirecting them to the study website page for more information. The CA will collect information on participants' responses to the program, including triggers to smoke (physical, emotional, and situational triggers), motivations to quit, barriers to quitting, and number of cigarettes smoked in end-to-end encrypted "private conversations", and it will not collect PHI. Data will also be collected on usage information: the number of days user interacted with assigned intervention and whether users completed assigned intervention. This information will be extracted over a secure connection on a weekly basis, and stored on a secure internal Fred Hutch server. A raw copy of the data serves as an additional backup beyond the ongoing built-in Azure storage backup processes. An automated script creates a fully de-identified and cleaned copy of the data, to send to the study team analysts. This usage data can be tied to the survey data using the aforementioned randomly generated opt-in IDs.

**SmokefreeTXT utilization data and security.** Participants randomized to the SmokefreeTXT arm will be asked to provide a quit date on a website with data transmission via Transport Layer Security (TLS.) A schedule of text messages is set up based on the quit date. Participants can request that messages be stopped at any time. Date stamps and content of the outgoing messages and incoming messages with participant responses to queries about mood, cravings, relapse, and smoking status will be stored on secured Fred Hutch servers. These data will only be accessible to Fred Hutch Shared Resource programmers and not accessible via websites. The programmers will prepare de-identified utilization data for analysis.

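### The serial mediation model treats alliance as the cause of engagement, but alliance is first measured after most scheduled use and no time window for engagement is set, so the direction of d21 is not identified; the equations also name no baseline covariates

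*Combined protocol and SAP*

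**What the plan says.** Section 11.3 sets out a serial model from arm (X) to therapeutic alliance (M1) to engagement (M2) to 12-month cessation (Y). The key link is that "the therapeutic alliance processes will in turn impact treatment engagement variables". Three equations summarise the model: M1 on X; M2 on X and M1 (coefficient d21); Y on X, M1 and M2. They are to be fitted with PROCESS and bootstrap intervals. None contains a baseline variable.

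The timing is spread over several sections:

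- Section 11.1 (and 3.3) measures "mediators at 3 and 6 months post randomization".
- Section 10.1 places alliance after baseline: "The 3-month survey will primarily collect data on intervention processes (e.g., therapeutic alliance), cessation progress". The baseline survey list in the same section has no alliance measure.
- Section 7.1: "Both therapies (the digital intervention programs) consist of 42 days of smoking cessation content".
- Section 10.1 describes the logged QuitBot use as "the number of days user interacted with assigned intervention and whether users completed assigned intervention", without a start or end date for the count.
- Section 7.0 lets use run late, "with those not responding to prompts continuing where they left off".

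Section 11.5 mentions covariate adjustment for Objective 2 once. It says that the power figure ignores any gain from it and gives the stratification factors as the example. By contrast, section 11.2 states that the primary model adjusts for those factors.

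**The concern.** Path d21 is read as the effect of alliance on engagement. If alliance is recorded at 3 months and most of the engagement it is meant to cause was scheduled for the first six weeks, a positive d21 fits the opposite story equally well: people who used the program more, or who had already quit, rate the alliance higher. Nothing in the plan restricts M2 to use after alliance was measured, and no sensitivity analysis for the order is planned.

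Randomization protects the arm effects on each mediator (a1, a2). It does not protect d21, b1 or b2, which compare people who differ in motivation, dependence and much else.

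Objective 2 is meant to explain how conversational agents work and which communication processes to target. A significant serial path that could arise without the mechanism would not support that conclusion.

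**Working it through.** **The plan's own figure.** Section 11.5 claims more than 99% power for the three-path effect with 1,520 randomized and 85% follow-up. The analysed number is 1,520 × 0.85 = 1,292. Reading 0.14 as a correlation on each path, joint-significance power is Φ(0.14·√1292/√(1 − 0.14²) − 1.96)³ = Φ(3.12)³ = 99.7%; a percentile-bootstrap simulation gives 99.5%. The figure reproduces on that reading. It is power to detect an association and says nothing about direction.

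**Inputs for the reverse-order check.**
- From the documents: n = 0.85 × 1,647 ≈ 1,400; 1:1 allocation; two-sided 5%; mean quit rate (9.3% + 13.9%)/2 = 11.6%.
- Assumed: arm effect on engagement δ = 0.14 to 0.4 SD; link k from engagement to later alliance 0.2 to 0.4; log-OR 0.4 per SD of engagement on quitting; no direct arm effect on alliance; one variable per mediator.

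True d21 is zero. The data follow M2 = δX + e and M1 = kM2 + e, with unit error variances.

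**Formulas.** The path is declared significant when a1, d21 and b2 all exceed |z| = 1.96.
- a1: z = kδ / (2√(1 + k²)/√n)
- d21 (spurious): z = k√n, which is 7.5 at k = 0.2 and 15.0 at k = 0.4, so practically always significant
- b2: the SE is about √(1 + k²)/√(1,400 × 0.116 × 0.884) = 0.0835√(1 + k²), so z is 4.7 at k = 0.2 and 4.5 at k = 0.4, significant in over 99%

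The rejection rate is therefore close to the power of a1, Φ(z − 1.96). At k = δ = 0.4, z = 0.16/0.0576 = 2.78, which gives Φ(0.82) = 79%.

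| k | δ (SD) | z for a1 | closed form | simulated (1,000 trials) |
|---|---|---|---|---|
| 0.4 | 0.40 | 2.78 | 79% | 81% |
| 0.4 | 0.28 | 1.95 | 49% | 49% |
| 0.4 | 0.14 | 0.97 | 16% | 15% |
| 0.2 | 0.40 | 1.47 | 31% | 33% |
| 0.2 | 0.28 | 1.03 | 17% | 20% |
| 0.2 | 0.14 | 0.51 | 7% | 9% |

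Across all runs the range is about 7% to 82%.

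**If the arm also affects alliance directly.** Simulations at n = 1,292 (arm effect on engagement 0.28 SD, log-OR 0.45 per SD, links 0.1 to 0.5) give 81.0% to 99.95% with a direct effect of 0.14 or 0.28 SD. With no direct effect they give 7.5% to 71.8%. The clean null (no reverse order, no confounding) rejects in 5.6%.

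**Confounding of the two-path effect.** Assume a baseline trait with correlation r to engagement and log-OR g per SD on quitting, unrelated to alliance, with no true mediation and an arm effect of 0.4 SD on engagement. The unadjusted b2 is about r·g, with SE 0.0835.
- r = 0.3, g = 0.5: 0.15/0.0835 = 1.80, and Φ(1.80 − 1.96) is about 44% (simulated 43%; 4% after adjusting for the trait).
- r = 0.2, g = 0.3: 0.06/0.0835 = 0.72, giving about 11% over both tails (simulated 12%; 5% adjusted).

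These rates are for a2·b2. In the stronger scenario the serial path a1·d21·b2 is significant in only about 1% to 2% of trials, because d21 is null there.

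**Confounding of the serial path.** This needs a common cause of both mediators. At n = 1,292, with links of 0.2, 0.3, 0.4 and 0.5 to each mediator, the serial path is falsely significant in 31.2%, 89.8%, 99.8% and 99.9% of trials unadjusted. It falls to 4.9% to 5.4% when that cause is measured and adjusted for.

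**Covariates do not repair the order.** Under reverse order with link 0.3, adding a baseline covariate alone leaves the rejection rate at 99.4%.

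**The case against.** The strongest reply is that engagement need not end at day 42. Section 7.1 limits content, not use: the app is available at any time after randomization (section 2.4.2), help is on demand, and non-responders resume where they stopped (section 7.0). Mediators are also measured at 6 months, so later use could follow 3-month alliance. This stands. A reader might infer that d21 simply regresses an earlier variable on a later one; the documents support only that most scheduled use precedes the alliance measure and that the window for M2 is unspecified. The conceptual figures and a section C.7.2 cited in section 11.5 are not in the text available here and might add timing detail.

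On covariates, section 11.3 says the equations summarise the model, and section 11.5 hints that adjustment for stratification factors was contemplated. A reader might infer that adjustment was ruled out; that goes too far. The supportable criticism is that no covariate is specified.

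A reader might also carry the 12% to 43% confounding figures over to the serial path. They do not apply to it. Nor is any single reverse-order rate informative, since the result moves with assumed inputs and the checks use one variable per mediator where the plan has four and three.

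Finally, reversing the order outright would exchange one unidentified order for another, because alliance formed during the program could still drive use. That also stands and shapes the fix.

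**Conclusion.** The concern holds in this form: the planned serial path cannot distinguish alliance driving engagement from engagement driving later-reported alliance, and the mediator and outcome paths have no specified protection against confounding. With true d21 = 0 and the arm affecting alliance only through engagement, false support for the serial path runs from about 7% to 82% at n = 1,400, and higher with a direct arm effect on alliance. The missing covariates put the two-path effect a2·b2 at about 12% to 43% false significance in the scenarios run, against about 5% adjusted.

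All link strengths are assumptions, so the ranges show what is possible and do not predict this trial's result. A reader might infer that the trial's main result is in doubt. It is not: Objective 2 is secondary, the plan does not call d21 confirmatory, and the primary comparison does not use these equations.

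**What to change.** (a) Keep the planned serial model, but define the start and end of the period over which M2 is counted, relative to the alliance measurement. Report beside it either the reverse-order model (engagement, then 3-month alliance) or a parallel-mediator model. State in advance that a significant a1·d21·b2 is an association and does not establish that alliance causes engagement.

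(b) Add sex, heaviness of smoking index and confidence in being smoke-free to all three equations, with prespecified baseline variables already collected, for example nicotine dependence, readiness to quit, trust and social support. Say plainly that this handles measured confounding only and does not repair the time order.

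No new data are needed. The cost is SAP wording, a few more models to report, and a weaker mechanistic claim for Objective 2.

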Based on our successful methods for national recruitment [84], we developed and targeted FB ads with ongoing monitoring and adjustment of recruitment yield. These efforts yielded 1853 participants screened, 974 eligible, 452 consented, and 306 randomized (153 in each arm). Based on evidence from text messaging trials meta-analyses [1], we stratified randomization on biological sex (male vs. female), heaviness of smoking index score ( $\leq 4$  vs.  $>4$ ), and percent confidence in being smoke-free in 12 months ( $\leq 70\%$  vs.  $>70\%$ ). The two conditions were balanced at baseline on all measured characteristics (all p-values  $> .05$ ). Participants were mean age 36.3, 67% female, 28% minority, 52% unemployed, 43% high school or less education, 69% smoking at least half pack daily, and 59% high nicotine dependent. The characteristics of this FM sample are very similar to those of m/e-health trials [1, 2, 7]. To maximize outcome data completion, we followed our team's successful protocol [84]: four sequential survey modalities (first Web, followed by phone, mail, and postcard). Participants received \$25 for submitting their responses, and received an additional \$10 bonus for completing the Web survey within 24 hours. The achieved outcome survey completion rate of 93%, provided confidence in the follow-up survey methods. The data retention did not differ between study arms ( $p = .374$ ). For example, the point estimate for the number of days from randomization to the last user input showed that QuitBot participants engaged 26.3 (95% CI: 19.7, 33.0;  $p < .001$ ) days longer than SFT participants. QuitBot's intervention completion results are substantial when considering that each day's content involves a 3 to 5-minute conversation. The 30-day point prevalence (missing=smoking) abstinence rates at three-month follow-up (primary outcome) were 32% for QuitBot vs. 23% for SFT (OR = 2.18; 95% CI: 1.08, 4.39;  $p = .030$ ). Results for the secondary outcome of cessation from cigarettes and all other nicotine or tobacco products (except FDA-approved nicotine replacement) were promising.

Building on these promising results, a comparative effectiveness randomized trial with a fully-powered sample size (N = 1647) and longer-term follow-up (i.e., 12 months) is now needed to determine whether QuitBot: (1) provides higher quit rates than SmokefreeTXT, (2) operates according to therapeutic mechanisms of change, and (3) is cost-effective vs. SmokefreeTXT.

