11.5 Sample Size and Power

We determined sample size for binomial proportions aimed at 80% power for Primary Objective 1 using the following parameters: (1) randomized to one of the two interventions; (2) conservative 12-month outcome survey response rate of 85%, based on our most recently published large RCT comparing two digital interventions [84]; (3) 80% completion rate of biochemical verification [103, 104]; (4) intent-to-treat analysis where, as standard in digital intervention smoking cessation trials, all those with missing data (including missing biochemical data) are coded as smokers [1, 121]; and (5) two-sided test with  $\alpha = .05$ . We adjusted all power analyses for expected non-response rates and biochemically-confirmed cessation rates so that outcomes would not be inflated.

Power for Objective 1: Objective 1 will compare 12-month quit rates between QuitBot vs. SFT. Projected quit rates at 12-month follow-up were conservatively calculated using (1) quit rates at 3-month follow-up in our pilot RCT, along with (2) well-established relapse curves, which provide a data-derived estimate (i.e., 20-35%) of the rate of decay of intervention effects by 12-month follow-up [90, 91, 122]. We estimated a relapse of 27% (between 3 and 12 month-follow-up) and survey response and biochemical verification completion rates of 85% and 80%, respectively. The 12-month quit rate for SFT is conservatively estimated as 9.3%, as consistent with the projected SFT 12-month relapse rates from the pilot RCT and the 8.4% average quit rate from the most recent meta-analyses [1, 2, 18-21]. As shown in Table 5, obtaining 80% power to significantly detect a quit rate as low as 13.9% for QuitBot (vs. 9.3% for SFT) requires 1,520 randomized participants, with 760 in each study arm.

Table 3. Objective 1 Sample Size Estimates.

	Projected relapse rate				
	20%	25%	27%	30%	35%
	QuitBot 12-month follow-up 30-day point prevalence quit rate				
	15.2%	14.3%	13.9%	13.3%	12.4%
Total in each arm	484	653	760	983	1,579
Total randomized	968	1,306	1,520	1,966	3,158

This very conservatively estimated 13.9% quit rate would have high public health impact—49% higher impact than the projected 9.3% quit rate for SFT and 65% higher than the average 8.4% quit rate observed in text messaging interventions [1, 2, 18-21].

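### The Objective 2 mediation model inherits the missing-equals-smoker outcome with no imputation check, so engagement can look like a mediator if engaged participants are likelier to answer the survey or complete the saliva test

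*Combined protocol and SAP*

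**What the plan says.** - **Mediation outcome.** Section 11.3 makes the 12-month primary endpoint the outcome Y in its third equation. Path b2 is the hypothesis that "the engagement variables will in turn impact the 12-month primary cessation outcome". The section will also report the share of the treatment effect explained by each mediator.
- **Missing data.** Section 11.2 states that "all missing outcomes will be coded as smokers". Section 11.5, among the Objective 1 sample-size parameters, goes further: "all those with missing data (including missing biochemical data) are coded as smokers".
- **Sensitivity analyses.** Section 11.2 lists "multiple imputation of missing outcomes" and "complete case analysis of those providing follow-up data". They follow a model introduced with "For each comparison of the treatment arms on the primary and all secondary endpoints". Neither section 11.3 nor the Objective 2 power text in 11.5 states a missing-data rule or sensitivity analysis for mediation.
- **Engagement data.** Section 10.1 collects usage automatically in both arms, so it exists for people who never return a survey.
- **Who is tested.** Section 11.2 says "biochemical confirmation will be conducted on participants self-reporting no smoking at all in the last 30 days". Section 10.1 describes testing a random 10% of participants, selected at randomization.

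**The concern.** Coding missing as smoking is a convention for comparing randomized arms. Path b2 is a different quantity: a non-randomized association, within arms, between engagement and recorded abstinence. Someone who stops using the programme may also be likelier to ignore the 12-month survey or skip the test. That person has a low engagement score and is recorded as a smoker whatever the truth. Path b2 then partly measures willingness to respond.

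The pilot suggests that QuitBot raises engagement substantially, so path a2 offers little protection: a spurious b2 passes almost directly into the indirect effect. The protocol's rationale is that low engagement holds back quit rates, and this analysis could appear to confirm it when engagement had no effect.

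**Working it through.** **1. The plan's own figure.** Section 11.5 gives 760 per arm for 13.9% vs 9.3%, two-sided 0.05, 80% power. With mean rate 0.116:

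n = [1.96·√(2·0.116·0.884) + 0.842·√(0.093·0.907 + 0.139·0.861)]² / 0.046² = 759.6, so 760.

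The other Table 3 columns (484, 653, 983, 1,579) also reproduce.

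**2. How much of the outcome is coded rather than observed.** Section 11.5 expects 85% response and 80% test completion. The share of true abstainers recorded as smokers is 1 − 0.85 × 0.80 = 32%. Section 11.5 says its rates are adjusted for both losses. Taking that as stated, implied true abstinence is 9.3/0.68 = 13.7% and 13.9/0.68 = 20.4%, average 11.6/0.68 = 17.06%.

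**3. Closed form.** Split 1,520 people at median engagement (760 per half), with the same true abstinence in both halves. Recorded abstinence = 17.06% × response × testing. The gaps are assumptions.

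| Response, high vs low | Testing, high vs low | Recorded | False odds ratio | Rejection |
|---|---|---|---|---|
| equal | equal | equal | 1.00 | nominal |
| 90% vs 80% | 80% both | 12.3% vs 10.9% | 1.14 | 13% |
| 90% vs 80% | 85% vs 75% | 13.1% vs 10.2% | 1.32 | 40% |
| 95% vs 75% | 85% vs 75% | 13.8% vs 9.6% | 1.51 | 72% |

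**4. The arm effect on engagement.** Section 2.3 reports that QuitBot users stayed engaged 26.3 days longer (CI 19.7 to 33.0), with 153 per arm. SE = 13.3/3.92 = 3.39; SD = 3.39/√(2/153) = 29.7; d = 26.3/29.7 = 0.89.

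**5. Simulated mediation model.** N = 1,647; true abstinence 20% and unrelated to arm, alliance or engagement; d about 0.9; sample limited to 3-month responders. False declarations of mediation by engagement, over repeated sets of runs:
- Response 88% vs 82%, testing 80% in both halves: 9% to 11%.
- Response 88% vs 82%, testing 84% vs 76%: 29% to 33%.
- Response 90% vs 80%, testing 86% vs 74%: 60% to 61%.

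The serial path through alliance and then engagement gave the same rates. A second design (N = 1,520, arm effect 0.5 SD, no restriction to 3-month responders) gave a false b2 odds ratio per SD of 1.07 with 11% rejection, rising to 1.21 with 64%. With a weak, response-only link (odds ratio 1.25 per SD) it gave 1.035 and 6.6%.

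**6. A small arm effect.** Section 11.5 powers the mediators at 0.14 SD. If 0.14 is the whole arm effect on engagement and alliance carries part of it, the a2·b2 path is falsely declared in about 1% to 10% of trials. If alliance carries none of it, the range is 7% to 35%. The serial path does not depend on a2, so it is not protected in this way.

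**7. The reported share.** With a true arm effect and no engagement effect, the median share of the arm effect that engagement appeared to explain was 21% (response 88% vs 82%, testing 84% vs 76%) and 34% (91% vs 79%, 85% vs 75%). The true share was zero.

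**8. What removes it.** Imputing non-responders with arm, engagement and alliance in the model, and keeping self-report for untested quitters, gave an odds ratio of 1.00 and 4% to 8% rejection. Complete-case analysis works when only survey response depends on engagement (about 5%). It leaves 8% to 14% when untested quitters are dropped and testing depends on engagement.

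**9. The testing conflict.** If only a random 10% were tested and every untested quitter counted as a smoker, recorded rates would be 13.7% × 0.85 × 0.10 = 1.2% and 20.4% × 0.85 × 0.10 = 1.7%. These cannot be squared with the planned 9.3% and 13.9%.

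**The case against.** **The coding rule reaches mediation only by reference.** Section 11.3 names the primary outcome and is silent on missing data. The biochemical rule sits in the Objective 1 sample-size text. A reader might infer that the plan expressly prescribes missing = smoker for Objective 2; it does not. Naming that endpoint as Y nevertheless brings its definition along, whereas the sensitivity analyses are attached to arm comparisons.

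**The key input is undocumented.** No section reports response or testing by engagement. Pilot follow-up was 93% with no difference by arm (p = .374) despite the large engagement gap, and section 7.2 collects outcomes outside the intervention with telephone, mail and incentives. This may well weaken the link. It does not exclude it, because the bias arises within arms.

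**The larger rates depend on testing.** The 30% to 60% figures need untested quitters coded as smokers and testing that depends on engagement. Random 10% selection would be unrelated to engagement. With no test-related missingness, rates were 9% (response 88% vs 82%) and 23% (90% vs 80%).

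**Other assumptions lower the rates.** If 3- and 12-month response are correlated at 0.5, the three scenarios in step 5 give 6%, 25% and 51%; at 0.8 they give 5%, 22% and 41%. If true abstainers respond at about 95% and testing is unrelated to engagement, rejection is about 4% to 6%. These points limit the size; they do not supply the missing safeguard.

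**Imputation does not make engagement causal.** Motivated people may both engage and quit, and the third equation has no baseline covariates. This stands.

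**Conclusion.** The concern holds conditionally. As written, the mediation model uses an outcome that would record about 32% of true abstainers as smokers, against a predictor that may be related to who responds, with no analysis to detect the resulting bias. Given an engagement effect on QuitBot of about 0.9 SD, false mediation runs at about 10% if only response differs (88% vs 82%), and about 30% to 60% if testing differs too and untested quitters count as smokers. It is near nominal under a weak link and lower for the path through engagement alone if the arm effect on engagement is small. All the gaps are assumptions.

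A reader might infer that any finding of mediation by engagement will be an artefact. The documents do not support that, because they give no evidence that response depends on engagement. Nor does this point bear on the primary arm comparison. It concerns a secondary objective and is worth correcting because the correction is cheap.

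**What to change.** In section 11.3:
- Fit the mediation model with multiple imputation of missing 12-month status. Include arm, engagement, alliance, stratification factors, 3- and 6-month smoking status, and self-reported abstinence for untested quitters in the imputation model.
- Report it beside the missing = smoker version.
- State that mediation by engagement will not be claimed unless it holds under imputation.

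Reconcile sections 10.1 and 11.2 on who is tested, since the size of the bias depends on it. Leave the primary arm comparison unchanged.

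The cost is SAP wording and modest programming, as section 11.2 already plans imputation. The imputed result rests on data being missing at random. It also leaves confounding between engagement and quitting in place, which the report should say.
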